10.3.3 Secondary outcome analysis

MMRM will be used to evaluate difference over time by treatment group in HRQoL outcomes. MMRM models will be adjusted for minimisation factors, treatment, baseline score, visit and a treatment by visit interaction as fixed effects, with patient included as a random effect. Differences between treatment groups will be reported as mean differences with 95% confidence intervals. Absolute and percentage changes in HRQoL outcomes from baseline assessment will be displayed graphically. HRQoL forms that are returned partially complete will be analysed according to the scoring instructions for each questionnaire.

Binary outcomes will be assessed using chi-squared tests and logistic regression analyses, adjusting for baseline and minimisation factors. Normality will be assessed for continuous outcome measures and differences between treatment arms will be assessed using a t-test or Mann-Whitney U test and presented as mean differences with 95% confidence intervals or median differences with interquartile range. Linear regression or GEE models will be used to adjust for baseline, minimisation and other important prognostic factors.

Survival analysis methods will also be used to compare differences between the treatment groups for overall survival (OS). Time to OS will be displayed using Kaplan-Meier plots.

Absolute (death rates at 12 months) and relative differences (hazard ratios) will be reported together with 95% confidence intervals.

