10 STATISTICS AND DATA ANALYSIS

10.1 Sample size calculation

The sample size is based on the primary outcome of change in AMS score from baseline to 6 months. Assuming a 6-month improvement in Δ AMS from a mean(SD) of 17(25) in the control arm to 28(25) in the intervention arm, allowing for 15 % patient loss to follow-up by 6 months (including patient death which is estimated to be around 2-3 % by 6 months), a total sample size of 222 patients is required with statistical power of 85 % and 2-sided significance level of 5 %. The assumed difference in Δ AMS and SD are based on our exploratory study [Phang et al., 2015] and are supported by data from the EMSCI database and other published series [Fehlings et al., 2016; WU et al., 2015] in which Δ AMS is between 15 – 18 with SD ranging from 15 – 25. There is expected correlation between the baseline and 6-month AMS scores, however there is no robust data on the strength of the correlation for patients with severe TSCI and thus we are unable to accurately account for this in the sample size calculation. By assuming no correlation, with the expectation that correlation is observed in the data, statistical power to detect a difference between the two treatment arms will be increased.

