10.3 Statistical analysis plan

This section provides a brief summary of the statistical analysis with full details being included in a separate statistical analysis plan (SAP). Full details of the statistical analysis will be detailed, in advance of un-blinding of the data, in a pre-specified SAP. The SAP will be written in accordance with the current OCTRU SOPs and will be agreed by the study statistician, the CI and the TMG.

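### Section 10.3.3 attaches an interquartile range, not a confidence interval, to the treatment difference for continuous secondary outcomes compared by Mann-Whitney

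*Protocol*

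**What the plan says.** Protocol section 10.3.3 covers continuous secondary outcomes in two sentences. The first sets the comparison: "Normality will be assessed for continuous outcome measures and differences between treatment arms will be assessed using a t-test or Mann-Whitney U test". The same sentence then fixes how the result is shown: "presented as mean differences with 95% confidence intervals or median differences with interquartile range". The natural reading pairs the mean difference with the t-test and the median difference with Mann-Whitney. The second sentence adds a model-based analysis: "Linear regression or GEE models will be used to adjust for baseline, minimisation and other important prognostic factors". It does not say how those estimates will be reported.

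Other results in the section have a proper interval. For quality of life, "Differences between treatment groups will be reported as mean differences with 95% confidence intervals". For overall survival, absolute death rates and "relative differences (hazard ratios) will be reported together with 95% confidence intervals". Section 10.3.1 uses medians with quartiles where they belong, to describe each group at baseline. Section 10.3 calls the whole statistical section a brief summary and leaves full detail to a separate SAP.

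**The concern.** A treatment difference needs a statement of how precisely it is estimated. An interquartile range gives the spread of patient values. It tends to a fixed number as the sample grows, whereas the uncertainty of a difference falls with the square root of the sample size. A reader who takes the interquartile range for an error bar will misjudge the evidence, usually by thinking it much weaker than it is.

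The outcomes exposed are the continuous secondary outcomes other than SF-36 that are sent to Mann-Whitney. Depending on their distributions, these could include grip strength, WISCI-II, SCIM-III, length of stay and the MRI lengths. Section 10.1 relies on the functional scales to show that a motor gain comes with a functional gain, so the precision of those differences matters.

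**Working it through.** **Inputs.** Section 10.1 assumes a "mean(SD) of 17(25) in the control arm to 28(25) in the intervention arm", that is, a difference of 11 and an SD of 25. It also gives 15% loss to follow-up, two-sided 5% significance, and totals of 222 (85% power) or 260 (90% power). Section 4 gives 1:1 allocation. The protocol has no SD for any secondary outcome, so using 25 below is an assumption that serves only to show scale.

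**1. The plan's own sample size, to fix the arm size.** n per arm = 2 × 25² × (z₀.₉₇₅ + z_power)² / 11².
- 85% power: 93 per arm, 186 in total, 186 / 0.85 = 219, against 222 stated.
- 90% power: 109 per arm, 218 in total, 218 / 0.85 = 257, against 260 stated.

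Both are reproduced closely, and nothing here disputes them. Evaluable patients per arm: 222 × 0.85 / 2 = 94.35, or 260 × 0.85 / 2 = 110.5.

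**2. Interquartile range (normal theory).**
- Within one arm: 2 × 0.6745 × 25 = 33.7.
- All pairwise between-arm differences: 33.7 × √2 = 47.7.

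Neither depends on n.

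**3. 95% confidence interval for the shift (Hodges-Lehmann).** Width = 2 × 1.96 × 25 × √(2/n) / √(3/π).

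| Evaluable per arm | 95% CI width | IQR, one arm | IQR, pairwise differences |
|---|---|---|---|
| 94.35 | 14.6 | 33.7 | 47.7 |
| 110.5 | 13.5 | 33.7 | 47.7 |
| 1,000 (hypothetical) | 4.5 | 33.7 | 47.7 |

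With about 94 per arm, the interquartile range is 33.7 / 14.6 = 2.3 times (one arm) or 47.7 / 14.6 = 3.3 times (pairwise) as wide as the confidence interval.

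**4. What a reader would see.** Suppose the estimated shift were 11. The confidence interval is 11 ± 14.6/2, or 3.7 to 18.3, which excludes zero. The pairwise interquartile range is 11 ± 47.7/2, or about −12.9 to 34.9, which includes zero. The same data give opposite impressions.

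**5. Skewed data.** Normal theory is a poor guide to a branch meant for non-normal outcomes, so the comparison was also simulated: 2,000 trials per distribution, 94 per arm, no true effect.

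| Distribution | HL 95% CI: mean width, coverage | IQR, one arm | IQR, pairwise differences |
|---|---|---|---|
| Lognormal (log-SD 0.8) | 8.3, 95.3% | 22.5 | 30.1 |
| Exponential (mean 17) | 6.3, 95.1% | 18.4 | 23.7 |

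The confidence interval does its job. The pairwise interquartile range contained zero in every simulated trial.

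**6. Does choosing the test by a normality check harm type I error?** In the same simulations, using Shapiro-Wilk to choose between the t-test and Mann-Whitney gave a type I error of 5.6% (normal data), 4.7% (lognormal) and 5.0% (exponential). There is no material inflation.

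**The case against.** The best defence is that section 10.3 presents itself as a summary, that section 10.3.1 shows the authors know what quartiles are for, and that the clause may be loose drafting for medians with quartiles by arm. That lowers the severity but does not remove the fault. The clause concerns differences between arms, and it is not left open for the SAP: it states a format, and a SAP that follows it inherits the error.

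A reader might also infer three stronger things that the protocol does not support.
- *The leading tests ignore the minimisation factors.* Section 10.3.3 names no leading analysis, and its next sentence plans linear regression or GEE with that adjustment. Only the ranking of the two is unstated.
- *These outcomes cannot be published with a valid interval.* The planned models can supply estimates with confidence intervals. The gap is that no reporting format is given for them.
- *The normality check must go.* The text says that normality will be assessed, which need not mean a formal test, and step 6 shows no material cost in type I error. A fair remark remains: the data may decide whether a mean or a median difference is reported. Removing the check is largely a matter of preference.

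It is also true that Mann-Whitney does not in general test a difference in medians. Under a location-shift model the shift is the median difference, so this gives no separate reason to fault the clause.

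**Conclusion.** The point stands as a reporting error of limited scope. For continuous secondary outcomes on the Mann-Whitney branch, the stated format gives the treatment difference a measure of patient spread instead of its uncertainty. That the interquartile range does not shrink with sample size holds whatever the outcome. The ratios of 2.3 and 3.3 are illustrative: they rest on the borrowed SD of 25, normal theory and about 94 evaluable per arm. The protocol gives no distributions, so which outcomes will take this branch is not known.

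Quality-of-life, binary and survival outcomes lie outside the clause. The primary analysis, sample size and type I error are unaffected.

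**What to change.** In section 10.3.3, and in the SAP:
- Replace the median-difference format with a Hodges-Lehmann shift (or a median difference) and its 95% confidence interval, naming which one is used.
- Keep medians with quartiles for describing each arm.
- State that the planned linear regression or GEE estimates will be reported with 95% confidence intervals, adjusted for the minimisation factors and for the baseline value where one is collected. The assessment table in section 7.7 and Appendix 2 show CUE-Q, grip strength, WISCI-II and SCIM-III at 6 months only, so these have no baseline score of their own.
- Leave SF-36 on its existing mixed-model route.

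One caution: where most patients score zero, the Hodges-Lehmann shift may itself be zero. Pseudomeningocele size could behave this way: section 2.1 reports one in 5 of 26 duroplasty patients, and patients without one might be scored zero (an assumption). For such outcomes the model estimate would be more informative.

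The cost is wording only, with no new data and no change to sample size. It is best done before unblinding.

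### Section 10.3.3 attaches an interquartile range, not a 95% confidence interval, to arm differences on the Mann-Whitney route

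*Protocol*

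**What the plan says.** Section 10.3.3 sends continuous outcomes through a normality check, after which "differences between treatment arms will be assessed using a t-test or Mann-Whitney U test". The results are then "presented as mean differences with 95% confidence intervals or median differences with interquartile range". Read in order, the t-test route gets a confidence interval and the Mann-Whitney route gets an interquartile range in the same place.

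The next sentence adds adjusted models: "Linear regression or GEE models will be used to adjust for baseline, minimisation and other important prognostic factors". It does not say how their results will be reported.

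The other effect formats stated in the section all carry a 95% interval. For quality of life, analysed by MMRM: "Differences between treatment groups will be reported as mean differences with 95% confidence intervals". Twelve-month death rates and hazard ratios are treated the same way. Section 10.3.1 uses medians with quartiles, but only to describe the arms at baseline.

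Section 10.3 sets the status of all this: "This section provides a brief summary of the statistical analysis with full details being included in a separate statistical analysis plan (SAP").

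**The concern.** The two arms are separate groups of patients (Section 4), so no patient has a treatment difference whose quartiles could be taken. An interquartile range could be computed from one arm's values or from all between-arm pairs. Either one describes variation among patients. Neither tells the reader how well the difference between arms has been estimated.

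The outcomes that may take this route matter to the trial's argument. Sections 3.3 and 10.1 rely on CUE-Q, grip strength, WISCI-II and SCIM-III to show that a motor gain comes with a functional gain. The MRI lengths and length of stay are also continuous and fall outside the quality-of-life rule. If any of them is judged non-normal, the unadjusted difference would be printed with a range that looks like an interval but is not one, beside normally distributed outcomes that carry real 95% confidence intervals.

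**Working it through.** **Inputs from the protocol**

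- Primary outcome assumption (Section 10.1): "from a mean(SD) of 17(25) in the control arm to 28(25) in the intervention arm". The difference is 11, and 11/25 = 0.44 SD.
- Attrition (Section 10.1): "allowing for 15 % patient loss to follow-up by 6 months".
- Sample size: 222 at 85% power, or 260 at 90% power, two-sided 5% (Section 10.1).
- Allocation 1:1, and a mechanistic subset of at least 25 per arm (Section 4).

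**Inputs not in the protocol.** No SD, interquartile range or distribution is given for any continuous secondary outcome, and the text does not say which interquartile range is meant. Widths below are in SD units under assumed shapes. The 15% loss is assumed to apply to these outcomes too.

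**Step 1: reproduce the stated sample size and get the evaluable number**

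- Normal approximation: n = 2(1.960 + 1.036)²/0.44² = 92.8, so 93 per arm; 186/0.85 gives 219.
- Two-sample t-test: 93.7, so 94 per arm; 94/0.85 = 110.6, so 111 per arm and 222 in total, as stated.
- At 90% power the t-test gives 109.5, so 110 per arm; 110/0.85 = 129.4, so 130 per arm and 260 in total, as stated.

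The evaluable numbers are therefore 94 and 110 per arm.

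**Step 2: width of the interquartile range, normal outcome**

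- One arm: 2 × 0.6745 = 1.35 SD.
- All between-arm pairs: 1.349 × √2 = 1.91 SD.

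**Step 3: full width of a 95% confidence interval**

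- Mean difference: 2 × 1.96 × √(2/n).
- Hodges-Lehmann shift: that width × √(π/3).
- Difference in medians: that width × √(π/2).

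**Step 4: ratios of interquartile range to confidence interval, normal outcome**

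| Per arm | CI width, Hodges-Lehmann | CI width, medians | One-arm IQR / CI | Pairwise IQR / CI |
|---|---|---|---|---|
| 94 | 0.59 SD | 0.72 SD | 2.3 / 1.9 | 3.3 / 2.7 |
| 110 | 0.54 SD | 0.66 SD | 2.5 / 2.0 | 3.5 / 2.9 |
| 25 | 1.13 SD | 1.39 SD | 1.2 / 1.0 | 1.7 / 1.4 |

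In the last two columns the first figure is against Hodges-Lehmann and the second against the difference in medians. From 25 to 110 per arm the Hodges-Lehmann interval narrows from 1.13 to 0.54 SD, while the one-arm interquartile range stays at 1.35 SD.

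**Step 5: other shapes, by simulation (600 runs each)**

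- Exponential or lognormal, 94 to 110 per arm: 1.9 to 4.2.
- Strong skew (gamma, shape 0.5), 94 to 110 per arm: about 2.1 to 5.6.
- U-shaped, 94 to 110 per arm: about 1.5 to 5.2.
- All shapes including normal, 25 per arm: about 0.8 to 1.9.

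**Step 6: the remaining reading.** If the phrase meant the quartiles of the sampling distribution of the difference, it would be a 50% interval with relative width 0.6745/1.96 = 0.34. That would be too narrow. None of these readings yields a 95% interval.

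**The case against.** The strongest reply is that this is shorthand in a section that calls itself a summary. Median and interquartile range are a familiar descriptive pair, Section 10.3.1 uses them correctly, and the analysis plan may spell out the interval. That is a plausible account of how the wording arose. It does not remove the problem: the sentence does not leave the interval open but names one, and the one it names is wrong. An analysis plan would have to repeat the error or depart from the protocol.

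The second reply is stronger. A reader might infer that these outcomes will have no valid interval at all, so that a harm could not be bounded. The protocol does not support that. The regression or GEE models in the next sentence apply to the same outcomes and yield an adjusted effect with a standard error. What stands is narrower: the unadjusted effect has no stated interval, and reporting of the adjusted one is not promised.

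A reader might also infer that a real benefit would be dismissed because the range covers zero. Nothing in Section 10.3.3 makes the interquartile range a decision rule. Significance comes from the Mann-Whitney test, which is unaffected.

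Finally, prescribing Hodges-Lehmann everywhere would be too rigid. WISCI-II, for example, may pile up at zero in AIS A to C patients (an assumption). In a simulation with 94 per arm on a 0 to 20 scale, with zeros in 60% of controls against 45% of treated patients, or 70% against 50%, the Hodges-Lehmann estimate was exactly zero in over 90% of runs. Mann-Whitney power was nevertheless just under 50% in the first setting and about 75 to 79% in the second. This objection stands, and the fix allows for it.

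**Conclusion.** The point holds as an error in a stated reporting rule. On the Mann-Whitney route the protocol puts a measure of patient spread where an interval for the treatment effect belongs.

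It concerns continuous secondary outcomes, other than quality of life, that are judged non-normal. These may include CUE-Q, grip strength, WISCI-II, SCIM-III, MRI lengths and length of stay. Which of them will take this route is not known, because the protocol gives no distributions. The primary analysis, the sample size, the SF-36 analysis and the survival results do not change.

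It is tempting to put a single figure on the error, such as two to four times too wide. The documents do not support one. The range of about 1.9 to 3.5 rests on normal data and 94 to 110 evaluable patients per arm, although this route is meant for non-normal data. Skew or a U shape moves it, and in the mechanistic subset, so far as this rule covers those outcomes, it falls to about 0.8 to 1.9. The firm conclusion does not depend on the ratio: an interquartile range is not a 95% confidence interval for a difference, whichever version is computed.

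**What to change.** In Section 10.3.3, and in the analysis plan if it repeats the phrase:

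- Replace the interquartile range on the Mann-Whitney route with a 95% confidence interval. Suggested wording: *median differences (Hodges-Lehmann, or difference in medians with a bootstrap interval where there are many ties, for example at zero) with 95% confidence intervals*.
- State that the adjusted effects from linear regression or GEE are also reported with 95% confidence intervals. This matters most when over half of both arms sit at zero, since both medians are then zero and their difference is uninformative.
- Keep the median and interquartile range as descriptive statistics within each arm.

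The cost is a sentence or two. No data collection, test or sample size changes, and the intervals are available in standard software. The change can be made without seeing any results.

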10.4 Subgroup analyses

Exploratory sub-group analyses will assess the impact of the minimisation factors under the treatment effect. Planned subgroup analyses will be specified in the SAP.

10.5 Interim analysis and criteria for the premature termination of the trial

No formal interim analyses are anticipated prior to completion of follow-up for the designated time points. The DSMC may request interim analyses at any point in the trial, which will be performed by the trial statistician. A DSMC charter will be in place for the DISCUS trial.

10.6 Participant population

The primary analysis population will be all randomised patients.

10.7 Procedure(s) to account for missing or spurious data

The number and percentage of individuals with missing data for each outcome at each time point will be summarised by intervention arm, along with reasons for missing-ness if known. The pattern of missing-ness will also be explored and the suitability of missing data assumptions considered.

The main analyses of the primary and secondary outcomes in this trial will be performed using the available case dataset. The impact of missing data on the results of the analysis of the primary outcome at the primary time point will be investigated. Missing data for the primary outcome is expected to be minimal (see 'Primary Outcome Analysis' section).

10.8 Economic evaluation

No economic evaluation is planned.

10.9 QRI data handling and analysis

All interviews will be audio-recorded, transcribed verbatim and edited to ensure anonymity of respondent. Data will be managed using NVivo software. Transcription will be undertaken by an approved transcription service/transcriber that has signed the necessary confidentiality agreements with the University of Bristol. All transcripts will be edited to ensure anonymity of respondent. Data will be managed using NVivo software and stored on encrypted drives at the University of Bristol, in line with the university's data storage policies and [current GDPR legislation](#).

Interview data will be analysed thematically using constant comparative approaches derived from Grounded Theory methodology [Strauss et al. 1994].

Audio-recorded recruitment consultations will be subjected to targeted transcription and subject to the same processes to ensure anonymity of participants as listed for interview data above. Transcripts will be subject to content, thematic, and novel analytical approaches, including targeted conversation analysis [Wade et al., 2009] and quasi-qual appointment timing (the 'Q-Qat method') [Paramasivan et al., 2015] as described in the QRI protocol [Donovan et al., 2016]. Triangulation across all these data will inform feedback to the DISCUS TMG (described in 7.9 above). De-identified quotes from interviews and audio-recorded recruitment consultations may be used in recruiter training within DISCUS and in publications.

At the end of the study, audio-recordings will be kept for at least 10 years before they will be destroyed. Transcripts will be stored indefinitely in secure research data storage designated 'controlled access', so can only be accessed by approved individuals who are interested in conducting their own analyses of the data. These individuals will have to submit an application to do this, which will be assessed by an independent committee. However, all data will have identifiable information removed before they are made available, and there will be no way to identify any individuals mentioned in interviews/appointments.

11 DATA MANAGEMENT

A Data Management and Sharing Plan (DMP) will be produced for the trial and will include reference to confidentiality, access and security arrangements. All data will be processed in accordance with data protection rules. Direct access will be granted to authorised representatives from the Sponsor, host institution and the regulatory authorities to permit trial-related monitoring, audits and inspections.

All trial data will be collected on trial specific documents, for example questionnaires and case report forms (CRFs). All trial-specific documents, except for the signed consent form and follow-up contact details, will refer to the participant with a unique study participant number/code and not by name. The participants will be identified by a participant ID number +/- year of birth on all study documents and any electronic database. Participant identifiable data will be stored separately from study data and in accordance with OCTRU SOPs. All trial data will be stored securely in offices only accessible by swipe

card by the central coordinating team staff in Oxford and authorised personnel. On completion of the study, and with appropriate participant consent, fully anonymised data may be shared with other organisations at the behest of the funder. All requests for the use of the data from the Discus study will be approved by the CI's and TMG. A data request form should be completed detailing the decision as to whether the request is accepted. In cases where individual site data is requested, only summary data would be provided with caveats for dissemination, to emphasise that trial data should be interpreted as a whole.

